Online RedCAP Recruitment: Immediately after clicking on the study advertisement, potential participants will be redirected to a separate secure RedCAP survey to review study information and complete self-screening. If eligible, prospective participants will be asked to provide their contact information. Those that are eligible will then be directed to the consent/assent and survey. Upon reviewing and completing this they are enrolled in the study and we will reach out via text with a unique link to take the baseline survey. Automatic reminders will then be scheduled for every two days for the following 10 days. We have uploaded a copy of our consent/assent video to the IRB SharePoint folder.

Our flyer will contain a basic overview of the study and a link to the initial screening on redcap.

Some participants require additional screening to ensure residency in the United States. During the enrollment process, our use of Discord revealed the IP addresses

of some participants to be outside of the United States.

We will create an additional survey that asks if they are in the United States while collecting their IP address and for any that do not meet these criteria will be removed and any data collected will be erased.

Additionally, any who do not complete the survey will also be removed and their data erased.

4. * Describe all compensation/incentives offered to participants and timing of these offers:

Participants will receive up to \$100.00 for participation in the study:

Part 1: \$35 for the completion of the baseline survey.

Part 2: Complete a follow up survey for \$65

This will be given via electronic gift cards.

5. Recruitment materials: (attach all material to be seen or heard by subjects, including advertisements and scripts)

Document	Category	Date Modified	Document History
View USResidencyVerification_SGMYTr.pdf(0.01)	Recruitment Materials	4/30/2024	History
View SGMYTRIALInitialScreen_SGMYTri.pdf(0.02)	Recruitment Materials	4/19/2024	History
View SOVA Year 2 Flyer.pdf(1)	Recruitment Materials	3/21/2024	History
View SGMY Study Video Script_Version_0.03.docx(3)	Recruitment Materials	12/6/2023	History
View IRB SGMY Study Year 2 Demo Advertisement(1)	Recruitment Materials	2/22/2023	History
View IRB SGMY Study Year 2 Advertisement.docx(1)	Recruitment Materials	2/8/2023	History

Study Aims

1. * Describe the purpose, specific aims, or objectives and state the hypotheses

to be tested:

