This intervention trial will use a randomized factorial trial design where each of the 96 participants is randomly assigned to one of 16 combinations of the four study mini-interventions (IPs). There will be 16 possible combinations for the four IPs. For example, one combination will include no IP, and one combination will include all four IPs, and four combinations will include only one of the IPs. The rest of the 10 combinations will include a combination of two or three of the IPs (e.g. IP 1 + 2; IP 1 + 2 + 3; IP 2 + 3; IP 1 + 3, etc.) With n=6 individuals randomly assigned to each of the 16 combinations, this will yield n=48 with a given IP versus n=48 without the given IP (averaging over other combinations of the other three IPs) for the test of each main effect.

- 3. Describe the primary and secondary study endpoints:**

The primary endpoints are feasibility, usability, and acceptability of the IP.

The secondary study endpoint is change in help-seeking intention.

- 4. Provide a description of the following study timelines:**

Duration of an individual subject's active participation:

1 month

Duration anticipated to enroll all subjects:

1 year

Estimated date for the investigator to complete this study (complete primary analyses):

4/30/2024

- 5. List the inclusion criteria:**

Adolescents ages 14-19 will be included if they provide their assent and/or consent if 18 or above; have access to a smartphone; have finished 6th grade; have access to and intellectual and physical ability to use the internet; fit demographic criteria (SGMY); and have symptoms of depression and/or anxiety that are mild or more severe (PHQ-8 and/or GAD-7 = 5 or above)

We will routinely monitor the sample to ATTEMPT to reach close to the following proportions based on recruitment and enrollment flow (e.g. if recruitment and enrollment flow is at a steady rate and we have reached the proportions below we may begin to exclude those being oversampled to obtain balance - because of the pilot nature of the study this may not be possible if recruitment flow is slower than anticipated)

50% ages 14-16 and 50% ages 17-19

50% identify as sexual minority but cisgender and 50% identify as not cisgender

at least 40% identify as a racial or ethnic minority

- 6. List the exclusion criteria:**

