We will report all baseline characteristics (with counts (%) or mean (SD), median (IQR)) by intervention group, and will follow all reporting guidelines of the CONSORT extension to randomized trials of nonpharmacologic treatment[Boutron 2017], including creating a CONSORT diagram for transparent reporting. The primary analyses for the intervention trial will use an analysis of variance (ANOVA) model[Collins 2014](or equivalently a linear model as defined in Equation 1) with the Likert scale response (1-7, which are expected to be normally distributed) for help-seeking intention as the primary outcome and the assigned treatment factors as the explanatory variables; each $x_j = 1$ if the participant is assigned to the j th IP, and $x_j = 0$ otherwise.

$(1)y = \beta_0 + \beta_1 x_1 + \beta_2 x_2 + \beta_3 x_3 + \beta_4 x_4 + \beta_5 x_1 x_2 + \beta_6 x_1 x_3 + \beta_7 x_1 x_4 + \beta_8 x_2 x_3 + \beta_9 x_2 x_4 + \beta_{10} x_3 x_4 + \beta_{11} x_1 x_2 x_3 + \beta_{12} x_1 x_2 x_4 + \beta_{13} x_1 x_3 x_4 + \beta_{14} x_2 x_3 x_4 + \beta_{15} x_1 x_2 x_3 x_4$ The main effect for the 1st IP, for instance, can then be defined as the contrast testing

$(\beta_1 + \beta_5 + \beta_6 + \beta_7 + \beta_{11} + \beta_{12} + \beta_{13} + \beta_{15}) - (\beta_0 + \beta_2 + \beta_3 + \beta_4 + \beta_8 + \beta_9 + \beta_{10} + \beta_{14}) = 0$, where the first set of 8 coefficients correspond to conditions with $x_1 = 1$, and the second set include $x_1 = 0$. We will also test two- and three-way combinations of the different IPs through similar contrasts. For instance, the test for having both the first and second IP (versus no for at least one of those two, averaging over other IP combinations) will be tested using the following contrast: $(\beta_5 + \beta_{11} + \beta_{12} + \beta_{15}) - (\beta_0 + \beta_1 + \beta_2 + \beta_3 + \beta_4 + \beta_6 + \beta_7 + \beta_8 + \beta_9 + \beta_{10} + \beta_{13} + \beta_{14}) = 0$.

While the linear model and factorial design also allow for testing interactions, e.g. whether the effect of the first IP differs by presence or absence of the second IP, these effects were of less interest for our hypotheses, and will therefore only be considered as exploratory analyses. The other outcome measures and exploratory analyses and can be tested in the same manner with the above linear model. Normality of outcomes will be

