Those individuals who provide consent will be redirected to complete an online survey over RedCAP. Data will be captured on demographics including age, sexual identity, gender identity, race, ethnicity, education, parent/guardian support, homelessness, socioeconomic and social status, transportation access, prior mental health treatment, whether they have a PCP, health insurance status, access to mental health professionals as determined by county and HRSA Health Professional Shortage Area score, and past discriminatory experience by a mental health provider. Mechanistic and outcome survey constructs will at baseline assess: mental health personal and perceived stigma, SGM stigma (internalized homophobia and transphobia), attitudinal barriers toward seeking therapy, antidepressant outcome expectations, expectance of rejection due to SGM, concealment of SGM from others, confidentiality concerns, brief depression/anxiety knowledge, emotional support, help-seeking intention from multiple sources, a single help-seeking intention Likert scale likelihood question (i.e. 'I intend to seek help from a counselor or therapist for my mental health problems' scale 1-795), perceived need, actual help-seeking, depression symptoms (PHQ-8), anxiety symptoms (GAD-7), social isolation (UCLA scale), and perceived health (SF-12). Once the baseline survey is completed, then the participant will be provided with information that the research team will contact them soon with next steps.

Randomization

Once the adolescent completes the baseline survey, RedCAP software will be used to conduct randomization. For those who do not complete the baseline survey, they will not be randomized. The randomization schema will be pre-determined by the study statistician using the RedCAP randomization module. There will be 16 groups to be randomized to with 6 individuals randomized to each group. The mini-interventions or intervention principles (IPs) will be described below.

Intervention

Each individual will be invited to join a private virtual Discord server (<https://discord.com>). They will be asked to create a new Discord account for purposes of participating in the study which does not include any identifiable contact information.

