IP 3 Description: Difficulty with garnering parent or guardian support of mental health and LGBTQ status. Finding the words to communicate with their parent, or for themselves regarding names and identities for how they feel. Anticipating dismissal of their concerns and how they can find other supportive adults who can help them navigate communicating with a parent or guardian. Specific resources that they can offer to their parent (i.e. support groups, reading material, professionals) so their parent can receive assistance navigating their child's LGBTQ status instead of them having to educate their parent.

IP 4 Description: Finding affirming professionals. How to identify whether mental health professionals are competent in working with LGBTQ+ youth. Reviewing resources that help to identify mental health friendly spaces online. Reviewing what questions they can ask of a provider or a healthcare setting to know whether they would be affirming. What the law says about conversion therapy.

The research team will moderate all online discussions and provide feedback to individuals to guide them to factual information that can help answer their questions. Individuals will be prompted by text message each week to remind them to contribute to the Discord community.

Follow Up Survey (1 month)

All randomized individuals will receive a follow-up survey 30 days after they complete the baseline survey. Mechanistic and outcome survey constructs will be repeated in this survey. Additionally, in all but Group 1, we will measure Feasibility (i.e. proportion of IP tasks completed, length of time IP used); Usability utilizing the System Usability Scale (SUS); and Acceptability using open-ended questions regarding whether each IP group was helpful, affirming of SGM status, if timing and amount of content were appropriate, if privacy and confidentiality were maintained, and if they had any negative consequences of participation (e.g. parent questioning them).

Participants will be compensated for each research activity as described in compensation.

2. Upload a copy of all materials used to collect data about subjects: (Attach all surveys, interview/focus group scripts, and data collection forms except for case report forms, SCID or KSADS):

Document	Category	Date Modified	Document History
View SMASI (Modified, using items 14-16) (1.0)	Data Collection	6/22/2023	History
View Global Unique Identifier Information.docx(0.01)	Data Collection	2/24/2023	History

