	Infrequent Risks	Breach of Confidentiality; Fatigue; Being "outed"
	Other Risks	No Value Entered
View	Research Activity	Participating on Discord Server
	Common Risks	Mild psychological disturbance if reflecting on prior difficult experiences with seeking mental health help or being part of LGBTQ+ community
	Infrequent Risks	Breach of confidentiality
	Other Risks	No Value Entered

- 2. *** Describe the steps that will be taken to prevent or to minimize risks:

We believe all aspects of the study involve no more than minimal risk. In daily life, many adolescents use applications on smartphones regularly without requiring parental permission.

The risk of breach of confidentiality is low as survey data will be identified by an individualized code and not the patient's name. Any data downloaded from RedCAP will be stored on a secure University of Pittsburgh server.

Discord is not encrypted and there is some risk that information could be intercepted, however we will explain these risks during the consent process and will also seek to minimize the sharing of any identifying information by participants. A research team will review all content on the Discord survey every weekday daily and remove any information that is identifiable or could be offensive to any other user. The Discord settings will be set to not allow private messaging between individuals to allow for monitoring of all content. Prior to joining Discord, each individual will be asked to agree to and review ground rules of participating which include acknowledging that the intervention does not provide crisis services, to maintain anonymity, to not bully, and that any content our team feels will be hurtful to others will be removed. Our research team has years of experience moderating online interventions on the sova.pitt.edu website and maintaining anonymity. Discord settings for all notifications of new content on the server will be sent to the study email.

- 3. Financial risks - will the subject or insurer be charged for any research required procedures?**

Yes No

- 4. Describe the steps that will be taken to protect subjects' privacy:**

We will ask participants to password protect their phone and email. When we send emails and text messages about the study (e.g. online surveys being due) we will use vague language to not identify the individual as being involved in a mental health study. E.g. "Hi, its [name]! :) Its time for your survey! here is the link: [LINK INSERTED HERE]"

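### 30-day PHQ-8 and GAD-7 are compared by IP without the baseline score already collected, which costs precision but, with a correct contrast and full follow-up, causes no bias

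*Combined protocol and SAP*

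**What the plan says.** Research Activities, item 1 (Baseline Survey) lists among the mechanistic and outcome constructs "depression symptoms (PHQ-8), anxiety symptoms (GAD-7), social isolation (UCLA scale), and perceived health (SF-12"). Under Randomization it adds: "For those who do not complete the baseline survey, they will not be randomized". For the 1-month follow-up, sent to everyone randomised, it says: "Mechanistic and outcome survey constructs will be repeated in this survey". Both scales are therefore measured twice, and the first measurement precedes allocation.

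Study Design, item 8 sets out Equation 1 for help-seeking intention: an intercept, the indicators x1 to x4, and all their products. That makes 16 coefficients and no covariate. The remaining outcomes are covered by one sentence: "The other outcome measures and exploratory analyses and can be tested in the same manner with the above linear model". The fallback for non-normal data (transformation, or another generalised linear model) adds no baseline term. Item 8's only stated use of baseline data is the table of characteristics by group; PHQ-8 and GAD-7 also serve as entry criteria in item 5.

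Change is mentioned for a different outcome only, in Study Design, item 3: "The secondary study endpoint is change in help-seeking intention". Nothing says that y is a change score for PHQ-8 or GAD-7.

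**The concern.** A symptom score at 30 days usually correlates with the same score a month earlier. A model that ignores the earlier score leaves that predictable part of the variance in the residual, so each IP estimate has a wider interval than the data require. The trial has 96 people in 16 cells of 6, and the plan's own detectable main effect is 0.58 SD, so the loss is worth avoiding when the covariate is already in the database.

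What is at stake is the width of the intervals for two exploratory scales. Item 3 names neither as a primary or secondary endpoint, and the protocol states that the IPs are not treatments.

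**Working it through.** **Inputs from the documents.** 16 cells of 6; 48 with and 48 without each IP; 80% power; a stated detectable effect of 0.58 (Study Design, items 2 and 8).

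**Assumptions.** Two-sided 5% level (not stated, but it reproduces the plan's figure). Outcome SD set to 1. Baseline-to-30-day correlation r from 0.3 to 0.7 (not stated). Full follow-up, since the plan makes no allowance for loss.

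**Step 1: reproduce the plan.** SE of a 48 versus 48 difference = sqrt(1/48 + 1/48) = 0.204 SD. With the noncentral t on 94 df, 80% power is reached at 0.578, which rounds to the plan's 0.58. Equation 1 has 16 coefficients, so its residual df are 96 − 16 = 80, and the detectable effect is 0.579. Power for a true difference of 0.5 SD is 68%.

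**Step 2: add the baseline score.** Residual variance is multiplied by 1 − r², so SE = 0.204 × sqrt(1 − r²), on 79 df. A change score has SE = 0.204 × sqrt(2(1 − r)), on 80 df.

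| r | SE, covariate | Detectable, covariate | Power at 0.5 SD, covariate | Detectable, change score |
|---|---|---|---|---|
| none | 0.204 | 0.579 | 68% | – |
| 0.3 | 0.195 | 0.552 | 72% | 0.685 |
| 0.4 | 0.187 | 0.531 | 75% | 0.634 |
| 0.5 | 0.177 | 0.501 | 80% | 0.579 |
| 0.6 | 0.163 | 0.463 | 86% | 0.518 |
| 0.7 | 0.146 | 0.413 | 92% | 0.448 |

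Allowing for estimation of the slope (variance × (1 + 1/78)) moves the covariate column only to 0.556, 0.534, 0.505, 0.466 and 0.416. A change score is worse than the covariate at every r shown, and worse than no baseline at all below r = 0.5.

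**Step 3: which r is plausible here.** Entry requires 5 or more on PHQ-8 and/or GAD-7, which restricts the range. In simulation with assumed score distributions (PHQ-8 mean 11, GAD-7 mean 10, SD 5), an r of 0.6 fell to about 0.52 and 0.50 when everyone scored at least 5 on that scale. The middle of the table is then a fair guide.

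**Step 4: bias.** In 6,000 simulated trials per setting of the 2⁴ design with 6 per cell, full follow-up and a correctly coded contrast, a true effect of 0.58 was estimated as 0.578 to 0.582 without baseline and 0.579 to 0.581 with it. With no effect, both models rejected in about 4% to 5% of trials. The mean SE was 0.203 to 0.204 without baseline, against 0.195, 0.177 to 0.178 and 0.146 with it at r = 0.3, 0.5 and 0.7. Only the precision differs.

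**Step 5: the contrast needed.** Under 0/1 coding, averaging the 8 cell means with IP 1 and subtracting the average of the 8 without it gives b1 + ½(b5 + b6 + b7) + ¼(b11 + b12 + b13) + ⅛b15. Its SE is 0.204 SD, as in Step 1. The contrast printed in item 8 treats coefficients as if they were cell means ("where the first set of 8 coefficients correspond to conditions with" x1 = 1) and subtracts b0. With no IP effect it therefore equals −b0. Its SE is 0.913 SD. For an assumed mean of 10 and SD of 5 the expected statistic is −10/(5 × 0.913) = −2.19 when nothing is happening. The figures in Step 2 do not apply to it.

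**The case against.** The strongest reply is that these are peripheral scales. The plan states no symptom hypothesis and posits no 0.5 SD symptom difference, the wording on other outcomes is permissive, and the gain depends on a correlation the documents do not give. At r = 0.3 the detectable effect moves only from 0.58 to about 0.55 SD. All of that stands and sets the weight of the point. It does not remove the point, because the covariate is free. It is also fair that Equation 1 omits baseline for help-seeking intention too. The same adjustment could be considered there, once the plan says whether that y is a 30-day score or a change.

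Four stronger readings are tempting, and the documents do not support them.

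- *The planned comparison is biased for want of a baseline term.* Allocation follows the baseline survey, so with a correct contrast and full follow-up it is not. The qualification matters: the plan states no missing-data method. In an illustrative simulation with about 24% dropout related to baseline in opposite directions with and without the IP, the unadjusted completer estimate was off by 0.12 to 0.28 SD and the adjusted one by almost nothing. Dropout related to baseline equally on both sides gave no bias. Nothing in the documents predicts the first pattern.
- *The false-positive rate of the printed contrast shows the harm of omitting baseline.* Simulated null rejection of 60% to 77% comes from the intercept. Adding a centred baseline raises it to 78% to 88%, so baseline adjustment does not repair that error.
- *These contrasts measure the listed risk of taking part on Discord.* All participants are invited to Discord, and Group 1 has its own channel, so both sides of every IP contrast share that exposure.
- *Follow-up non-completers are erased.* Recruitment Methods, item 3 says "any who do not complete the survey will also be removed and their data erased", but the sentence before it introduces the US-residency survey, which is the natural referent. The promised CONSORT diagram should show losses by group.

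**Conclusion.** The point holds as a modest matter of precision. The only analysis that reaches 30-day PHQ-8 and GAD-7 leaves out a baseline score that nearly every randomised participant should have. For a correctly coded main effect with full follow-up, using it lowers the detectable difference from 0.58 SD to between about 0.55 SD (r = 0.3) and 0.41 SD (r = 0.7), or about 0.50 SD at r = 0.5. The fact of the omission is certain from the text. The size of the loss rests on the assumed correlation, the two-sided 5% level and complete data. The change is worth making but not essential, and no primary or secondary result depends on it.

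**What to change.** In Study Design, item 8, add wording to this effect: 30-day PHQ-8 and 30-day GAD-7 will each be analysed, as exploratory outcomes, with Equation 1 plus the mean-centred baseline score of the same scale. Each IP effect is the mean of the 8 cell means with that IP minus the mean of the 8 without it, reported with a 95% confidence interval. For IP 1 under 0/1 coding this is b1 + ½(b5 + b6 + b7) + ¼(b11 + b12 + b13) + ⅛b15; the equivalent is to code the factors −1/+1, test the IP term and double its coefficient. Do not use the contrast now printed in item 8.

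Participants may skip items (Waiver/Alteration of Consent, item 2), so a few baseline scores may be missing. Fill these with a simple value such as the overall baseline mean, so that no randomised participant is dropped for that reason.

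The cost is a few sentences and one residual degree of freedom (80 to 79), with no new data, survey or visit. If outcome data have already been seen, label the adjusted analysis post hoc.

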Even when online interventions exist, real-world uptake is low. Lack of engagement in online interventions is a known concern. Unfortunately SGMY who actively engage in online support interventions still experience low rates of mental health help-seeking. Targeted interventions are needed to address unique factors like double stigma (mental health and SGM status) in SGMY preventing help-seeking.

For the past 7 years, our team has used iterative stakeholder-informed approaches employing human computer interaction (HCI) techniques to design interventions directed at modifiable targets such as stigma and social support to enhance depression and anxiety treatment initiation in adolescents. In this project we plan to use an efficient approach to technology intervention design. Based on the Behavioral Intervention Technology Model, we will study intervention principles (IPs), or theoretical concepts including intervention aims and behavioral strategies, to understand which mechanisms of action hold promise while iterating on user design. The overall goal of the proposed project is to develop and test the usability, feasibility, and acceptability of an online intervention to increase help-seeking behavior among SGMY. Specifically we will use the HCI framework, Discover, Design/Build, and Test (DDBT).

We have completed a qualitative study with 25 SGMY to understand their needs for a mental health help-seeking intervention and found that the main topics that serve as barriers to seeking care include concerns about multiple identities and how those conflict with help-seeking; confidentiality and privacy concerns; having difficulty with

garnering parent or guardian support for mental health and/or LGBTQ status; and the process of finding affirming professionals. Adolescents were interested in intervention modalities to include online peer-led support groups, resource lists, and digital storytelling.

Study Design

- 1. Total number of subjects to be enrolled at this site (enter -1 for chart reviews, banking, registries):**

200

- 2. Describe and explain the study design:**

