The Discord server is similar to a Microsoft Teams or Slack where there are different channels available for different individuals. Each user, based on which Group they were randomized to will have access to a different set of channels which allow them to view their assigned intervention. All participants will be asked to sign in at least once a week to Discord to review and complete intervention activities and will be prompted with a text message reminder. The Discord settings will be set to not allow private messaging between individuals to allow for monitoring of all content. Each individual will be asked to agree to and review ground rules of participating which include acknowledging that the intervention does not provide crisis services, to maintain anonymity, to not bully, and that any content our team feels will be hurtful to others will be removed. The research team will download and save Discord transcripts from text conversations.

There are four "mini-interventions" or IPs: IP1, IP2, IP3, IP4.

There will be 16 groups with iterations of these interventions as described below:

Group 1: No IP, only a specific discord channel that asks individuals to at least post once a week responding to a single question about what makes them interested in participating in research

Group 2: IP 1

Group 3: IP 1, IP2

Group 4: IP 1, IP 2, IP 3

Group 5: IP 1, IP 2, IP 4

Group 6: IP 1, IP 2, IP 3, IP 4

Group 7: IP 1, IP 3

Group 8: IP 1, IP 3, IP 4

Group 9: IP 1, IP 4

Group 10: IP 2

Group 11: IP 2, IP 3

Group 12: IP 2, IP 3, IP 4

Group 13: IP 2, IP 4

Group 14: IP 3

Group 15: IP 3, 4

Group 16: IP 4

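### Feasibility, a primary endpoint, has no stated data source or denominator; collected in the 1-month survey where it is described, it would cover only survey returners and could overstate uptake

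*Combined protocol and SAP*

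**What the plan says.** Study Design, item 3, states: "The primary endpoints are feasibility, usability, and acceptability of the IP". The only operational description is in Research Activities, item 1, under Follow Up Survey (1 month). That paragraph opens with "All randomized individuals will receive a follow-up survey 30 days after they complete the baseline survey", says the mechanistic and outcome constructs are asked again, and continues "Additionally, in all but Group 1, we will measure Feasibility". Feasibility is then specified as "Feasibility (i.e. proportion of IP tasks completed, length of time IP used", in the same sentence as the System Usability Scale and the open-ended acceptability questions.

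Three other places bear on this:

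- Research Activities, item 1, Intervention, sets the expected activity: "All participants will be asked to sign in at least once a week to Discord to review and complete intervention activities". It also says "The research team will download and save Discord transcripts from text conversations" but gives the transcripts no analytic purpose.
- Recruitment Methods, item 3, after describing an extra US-residency survey, says "Additionally, any who do not complete the survey will also be removed and their data erased". It does not say which survey is meant.
- Study Aims, item 2, acknowledges that "Lack of engagement in online interventions is a known concern".

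The analysis text in Study Design, item 8, models help-seeking intention. It gives no dedicated analysis of feasibility, no target for it and no rule for missing follow-up.

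**The concern.** Task completion and time used are measures of engagement. People who never joined Discord, or who stopped after a week, plausibly also return the 30-day survey less often. If feasibility is recorded only in that survey, missing data depend on the very quantity being measured, and those who disengaged leave the calculation. The figure then describes people who stayed, whereas a feasibility endpoint should describe everyone offered the intervention.

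The comparison between IPs is also at stake. An IP that drives people away could look as feasible as one that keeps them, because those it lost are not counted. The trial is meant to show which IPs hold promise, so this could affect which ones are carried forward.

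**Working it through.** **The plan's own figures.** The plan states no rate, target, precision or dropout figure for feasibility, so there is nothing of that kind to reproduce. Its detectable effect sizes at 80% power are 0.58 (48 v 48), 0.67 (24 v 72) and 0.87 (12 v 84). They do reproduce: a two-sample t-test at two-sided 5% (assumed, as no alpha is stated) gives 80.3%, 80.3% and 79.7%. They concern comparisons of means and do not bear on this point.

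**Denominators.** There are 16 groups of 6. Each IP appears in 8 groups, so 8 x 6 = 48 people are randomised to it. Fifteen groups contain at least one IP, so 15 x 6 = 90 people.

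**Formula.** Let r be the share returning the survey, and c_R and c_N the task completion in returners and non-returners.

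- Completion over all randomised = r x c_R + (1 - r) x c_N
- Figure from the survey alone = c_R
- Overstatement = (1 - r) x (c_R - c_N)

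None of r, c_R and c_N is in the documents. All values below are assumptions.

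**Illustration 1: c_R = 60%, c_N = 10% (a 50-point gap).**

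- 10% non-return: 0.9 x 60 + 0.1 x 10 = 55%; overstatement 5 points
- 20% non-return: 0.8 x 60 + 0.2 x 10 = 50%; overstatement 10 points
- 30% non-return: 0.7 x 60 + 0.3 x 10 = 45%; overstatement 15 points

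An IP with 10% non-return and another with 30% would both show 60% among returners, although the figures over all randomised are 55% and 45%. A 10-point difference disappears.

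**Illustration 2: c_R = 70%, varying the gap, n = 90.** Cells show completion over all randomised, with the overstatement in points.

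| Surveys returned | c_N = 70% | c_N = 35% | c_N = 0% |
|---|---|---|---|
| 90/90 | 70% (0) | 70% (0) | 70% (0) |
| 81/90 | 70% (0) | 66.5% (3.5) | 63% (7) |
| 72/90 | 70% (0) | 63% (7) | 56% (14) |
| 63/90 | 70% (0) | 59.5% (10.5) | 49% (21) |
| 54/90 | 70% (0) | 56% (14) | 42% (28) |

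Over these assumptions the overstatement runs from 0 to 28 points. It is zero if all return, if non-returners use the IPs as much as returners, or if completion is taken from platform records for everyone.

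**The case against.** The strongest reply is that the protocol never says feasibility is self-reported, recalled or limited to survey responders. In the key sentence, usability and acceptability each have a stated instrument and feasibility has none, so task completion and time used could be platform metrics read at one month. The uploaded instruments named in the protocol include the usability scale but no feasibility form, and the attached list of all measures, which is not shown, may name a source. This stands. A reader might infer that the plan relies on recall from responders and that uptake is therefore overstated; the documents do not establish either. Nor do they show that the Discord transcripts will go unused for this endpoint, since the protocol is simply silent on their purpose.

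A reader might also infer that the erasure sentence deletes everyone who misses the 30-day survey. It follows the residency check and may refer only to that, or to the baseline survey. The text does not settle it.

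The protocol also has partial safeguards. The follow-up survey pays $65, with no stated link to Discord activity, which may weaken the tie between disengagement and non-return. Retention and missing-data patterns are monitored, and a CONSORT diagram is promised. These may reduce non-return or make it visible, but none sets a denominator for feasibility.

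Finally, transcripts are an imperfect source. They hold text only, so they miss video viewing and reading of guides; moderators remove some posts; and someone who never joined has no transcript. These limits stand, and they restrict what the transcripts can measure to posted tasks.

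**Conclusion.** The concern holds in conditional form. A primary endpoint has no stated source, denominator or rule for non-return, and its placement points to the version most open to upward bias. If feasibility is collected in the survey, uptake could be overstated by (1 - r) x (c_R - c_N): 5 to 15 points for an assumed 50-point gap and 10% to 30% non-return, and zero under full return or no gap. The upward direction rests on the assumption that non-returners used the IPs less, which is plausible and consistent with the protocol's own remark on engagement, but not shown. The size cannot be derived from the documents. The change is still worth making, because a denominator of all randomised people protects the endpoint whatever the return rate turns out to be.

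**What to change.** 1. Define posted-task completion for each IP over all people randomised to it (48 per IP; 90 across the 15 IP groups). Count it from the saved Discord transcripts as prompts answered in that IP's channels divided by prompts assigned there. Score anyone who never joined, or shows no activity, as 0.
2. Fix the list of countable prompts for each IP in advance, state that Discord accounts are linked to study IDs, and say how posts removed by moderators are counted.
3. Keep viewing and time used as survey items. Report them as responders-only, with the survey return rate beside them, overall and by IP. Do not use the interval from first to last post as time used: a single post gives zero, and two brief posts four weeks apart give about 28 days.
4. State in Recruitment Methods, item 3, that the erasure rule does not apply to randomised people who miss the follow-up survey.

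The cost is some coding of transcripts the team already plans to save, plus a few sentences of protocol text. The downside is that posts miss silent viewing, so the figure is conservative. The responders-only viewing items beside it give readers the other side of the picture.
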